4.2 Treatment Administration

4.2.1 Treatment arm: Triamcinolone 0.1% Cream

Eligible patients will be randomly assigned to either the treatment group to receive topical triamcinolone 0.1% cream for application to the face, chest and back, or will be assigned to the control group to receive no preemptive treatment. Patients will be assigned to either group in a randomized manner, stratified according to Fitzpatrick skin type. Stratification group 1 will consist of patients with Fitzpatrick skin type I-III. Stratification group 2 will consist of patients with Fitzpatrick skin type IV-VI. The Fitzpatrick skin typing test is a numerical classification schema for human skin color, as explained below (Fitzpatrick TB. The validity and practicality of sun reactive skin types i through iv. 1988. Archives of Dermatology. 124(6):869-871.)

• Type I (scores 0–6) always burns, never tans (pale white; blond or red hair; blue eyes; freckles)

NU Study Number: *JNC06142016* Other Study Numbers: STU00203631; NU 16D05

- **Type II** (scores 7–13) usually burns, tans minimally (white; fair; blond or red hair; blue, green, or hazel eves)
- **Type III** (scores 14–20) sometimes mild burn, tans uniformly (cream white; fair with any hair or eye color)

- Type IV (scores 21–27) burns minimally, always tans well (moderate brown)
- Type V (scores 28–34) very rarely burns, tans very easily (dark brown)
- Type VI (scores 35–36) Never burns, never tans (deeply pigmented dark brown to darkest brown)

If the patient is randomized to the treatment group, then the study team has the option to distribute the study drug either in person during a clinic visit or by shipping the study drug to the patient after success registration. If shipping the study drug to the patient, then we will use a courier such as FEDEX that provides tracking information and overnight shipments are preferred. The packaging will be secure and tamper proof, and the patient's name and address information will be verified.

If in the preemptive arm, treatment with topical steroids will start within 3 days of initiation of the EGFR inhibitor drug and continue for 6 continuous weeks. Patients will be instructed to apply the topical steroid twice daily over the face, chest and back. Patients will document each day administration of their EGFRI drug (if a tyrosine kinase inhibitor, i.e. home oral administration) and study topical medication, as well as a daily chart indicating potential medication adverse effects, in a study diary. Upon enrollment in the study, patients will be given an instruction sheet (see Appendix 3) for application of the topical cream.

All patients will be instructed to adhere to the same skin treatment regimen, regardless of whether they are in the treatment or control arm, which will be administered beginning up to 3 days before EGFRI initiation until up to 7 days after EGFRI initiation and will be continued through week 6. The skin treatment regimen will consist of skin moisturizer applied to the face, chest and back daily in the morning on rising and nightly at bedtime; and sunscreen (PABA free, at least SPF 15, UVA and UVB protection) applied to exposed skin areas before going outdoors. Participants will track their application in a daily diary (see Appendix 2).

4.2.2 Control arm

Participants in the control arm will be asked to follow the daily skin treatment regimen of skin moisturizer and sun protection before going outdoors, and to chart their applications in a daily diary.

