9.3 Data Analyses Plans

The primary objective will be to assess and compare the incidence of rash in patients treated preemptively with topical steroids and control patients.

Proportions experiencing EGFRI-induced papulopustular eruption (any severity) by 6 weeks will be estimated and compared using the Mantel-Haenszel Chi-Square test to account for the stratification factor in the randomization procedure. A test for homogeneity will be performed to assess the adequacy of a common odds ratio (OR). Results will be summarized using an OR and 95% confidence interval. Supportive analysis will use a generalized estimating equations (GEE) approach, which will allow modeling of the proportion of patients with rash over time. Fixed factors for treatment group, time and the treatment group by time interaction will evaluate time differences in the proportion of patients with rash between the two treatment arms while accommodating repeated measures over time.

The secondary objective, maximum grade severity during the 6-week study period will be tabulated by treatment group and compared using the Cochrane Armitage test for trend.

Secondary endpoints will also include comparisons across the study arms to assess changes in quality-of-life scores from baseline, as measured by the FACT-EGFRI-18 questionnaire. FACT-EGFRI-18 scores will be presented as the median percentage from baseline. Scores at 6 weeks will be compared using the nonparametric Van Elteren test, which combines stratum-specific Wilcoxon Rank-Sum statistics with weights inversely proportional to stratum sizes. Differences in adherence to chemotherapy treatment over the 6 weeks will be compared across the two study arms using the Mantel-Haenszel Chi-Square test. The incidence of adverse events will also be compared across treatment arms with a Fisher exact test.

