Appendix 2: Daily Diary					
Subject ID Number: Fill in the date and time each time you apply the medication. Write in any side effects that you have while taking the medication. Please bring this drug diary with you to your follow up appointments.					
Drug A:	0.1% topical triamcinolone cream	Your oncologist:			
How often:	Twice daily	Phone:			
How much:	Apply to face, chest, and upper back	Your dermatologist:	[name]		
When:	Once in the morning and once in evening	[contact]		

Special instructions: Remember to rub the cream in completely before engaging in daily activities. Please remember to apply broad spectrum sunscreen before going outside, and to use daily moisturizer. If you skip or miss a dose of the triamcinolone, please write "skipped" or "missed" under Time applied.

Day	Date	Time applied	Is a rash present?	Symptoms and Location of Symptoms
	1/0/0010	0.45		
Ex:	1/2/2016	8:15am	☑Yes □No	Itching, redness, pustules or bumps
1			□Yes □No	
1			□Yes □No	
2			□Yes□No	
2			□Yes□No	
3			□Yes□No	
3			□Yes □No	
4			□Yes □No	
4			□Yes □No	
5			□Yes□No	

NU Study Number: *JNC06142016* Other Study Numbers: STU00203631; NU 16D05

5	□Yes □No	
6	□Yes □No	
6	□Yes □No	
7	□Yes □No	
7	□Yes □No	
8	□Yes □No	
8	□Yes □No	
9	□Yes □No	
9	□Yes □No	
10	□Yes □No	
10	□Yes □No	
11	□Yes □No	
11	□Yes □No	
12	□Yes □No	
12	□Yes □No	
13	□Yes □No	
13	□Yes □No	
14	□Yes □No	
14	□Yes □No	
15	□Yes □No	
15	□Yes □No	
16	□Yes □No	

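### Daily logging of oral EGFRI doses is instructed only in the steroid arm, yet adherence to chemotherapy is to be compared between arms with no stated data source

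*Combined protocol and SAP*

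**What the plan says.** **Steroid arm.** The relevant paragraph of 4.2.1 begins "If in the preemptive arm, treatment with topical steroids will start within 3 days" of starting the EGFR inhibitor. Within it stands the logging instruction: "Patients will document each day administration of their EGFRI drug (if a tyrosine kinase inhibitor, i.e. home oral administration) and study topical medication". The same sentence also asks these patients to keep a day-by-day note of possible side effects.

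**Both arms.** The next paragraph of 4.2.1 changes scope: "All patients will be instructed to adhere to the same skin treatment regimen, regardless of whether they are in the treatment or control arm". It covers moisturizer and sunscreen, and points participants to the Appendix 2 diary to track what they apply. It does not mention EGFRI doses.

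**Control arm.** Section 4.2.2 sets the control task: follow the regimen of "skin moisturizer and sun protection before going outdoors, and to chart their applications in a daily diary".

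**The form.** Appendix 2 lists triamcinolone as its only drug and instructs: "Fill in the date and time each time you apply the medication". Its columns are day, date, time applied, rash yes/no, and symptoms with location. There is no field for an EGFRI dose.

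**The analysis.** Objective 2.2.3 and endpoint 6.3.3 make adherence a between-arm comparison. Section 9.3 says: "Differences in adherence to chemotherapy treatment over the 6 weeks will be compared across the two study arms", by Mantel-Haenszel chi-square. None of these sections defines adherence or names its source. Section 10.4 lists the questionnaire and the subject diary as the raw data.

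**The concern.** A between-arm comparison is interpretable only if the outcome is ascertained in the same way in both arms. Here a daily prompt to record oral EGFRI doses is written for one arm and not for the other. There is no placebo, so patients know their arm and nothing masks the difference in recording. If the diary contributes to the adherence endpoint, the arms could differ in recorded missed doses while dosing is the same, or look alike while dosing differs.

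The stake is a listed secondary endpoint with a planned test. Section 1.2 gives better adherence to oncologic treatment as one of the hoped-for benefits of prophylaxis, so a spurious result in either direction would bear on that claim. Daily entries that controls were never asked to make cannot be recovered at analysis.

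**Working it through.** **1. Scope of the text**

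| Item | Steroid arm | Control arm |
|---|---|---|
| Told to log oral EGFRI doses daily | Yes (4.2.1) | No (4.2.2, or anywhere else) |
| Told to log infused EGFRI | No | No |
| Told to track moisturizer and sunscreen | Yes (4.2.1) | Yes (4.2.1, 4.2.2) |
| EGFRI-dose field on the Appendix 2 form | No | No |
| Adverse-effect assessment and diary review at weeks 2, 4, 6 (section 5.0) | Yes | Yes |

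The asymmetry is in the first row. The other rows are the same in both arms.

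**2. The plan's own figure.** No figure is given for adherence. The only powered comparison is rash, 75% vs 45%, two-sided 5%, 80% power. With mean rate 0.60 and pooled variance:

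n = [1.96·√(2·0.60·0.40) + 0.842·√(0.75·0.25 + 0.45·0.55)]² / 0.30² = (1.358 + 0.555)² / 0.09 ≈ 40.7, so 41 per arm.

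Power is 0.793 at 40 per arm and 0.813 at 42. This agrees with section 9.2, and 42 per arm is used below.

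**3. Illustration: how unequal recording could act.** The recording rates are assumptions; nothing in the documents supplies them. True adherence is equal. Let p₁ and p₂ be the proportions of patients recorded with any missed dose under two different recording methods. Stratification by skin type is ignored. With a and b recorded cases, n per arm, N = 2n and m = a + b:

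X² = (N − 1)·N²·(a − m/2)² / [n²·m·(N − m)], rejecting if X² > 3.84.

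The rejection probability is the sum of Bin(a; n, p₁)·Bin(b; n, p₂) over all rejecting pairs.

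| p₁ vs p₂ | n per arm | Rejects |
|---|---|---|
| 20% vs 20% (equal recording) | 42 | 0.052 |
| 20% vs 5%, all on oral agents | 42 | 0.595 |
| 20% vs 10%, all on oral agents | 42 | 0.259 |
| 20% vs 5%, oral-only subset, half of each arm | 21 | 0.311 |
| 12.5% vs 5%, whole arm, half on infused agents | 42 | 0.251 |

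The last row uses 5% recorded for infused agents in both arms. One arm then shows 0.5·20% + 0.5·5% = 12.5% and the other 0.5·5% + 0.5·5% = 5%. The apparent difference falls from 15 to 7.5 points.

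**4. A second set of assumptions.** Take 40 per arm, equal true non-adherence of 20% to 40%, full detection in one arm, and a normal approximation. If the other arm detects 75% of cases, the false-positive rate is 9% to 15%. If it detects 50%, the rate is 24% to 50%. With equal detection it is 5%.

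**5. Masking.** Suppose true non-adherence is 10% in one arm, fully detected, and 20% in the other, half detected. The recorded rates are 10% and 0.5·20% = 10%, and a real difference disappears.

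**The case against.** **Adherence may not come from the diary at all.** This is the strongest point, and it stands. No section names the diary as the source. If one set of treatment records served both arms, this bias would not arise. A reader might infer that the comparison will rest on diary data in one arm and clinic records in the other, but the documents do not say so. What remains is that no other record of EGFRI administration is described, and 9.3 does nothing to exclude the diary.

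**The form has no EGFRI field for anyone.** True. The steroid-arm instruction has no printed field behind it, so better capture in that arm is not assured. Adding the field alone would still leave controls without an instruction to complete it.

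**'Patients' in the logging sentence could mean everyone.** Possible, but the paragraph's opening words, the explicit change of scope in the next paragraph, and the separate task in 4.2.2 all point the other way.

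**Direction.** A reader might infer that the bias runs against the cream, because a daily prompt finds more missed doses. Self-report could equally understate them. The documents do not settle the sign.

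**Rash and symptoms.** A reader might infer that controls would leave the rash and symptom columns empty. The text does not support that. The all-patients paragraph sends controls to the same form, the form mentions sunscreen and moisturizer, and the visit assessments in section 5.0 apply to both arms. No rash endpoint is said to come from the diary. The form is awkwardly worded for controls, and no more than that.

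**Infused agents.** Section 4.4 allows cetuximab and panitumumab, which the logging sentence leaves out in both arms. They dilute any bias in a whole-arm comparison, as the last row of the first illustration shows.

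**Conclusion.** The point holds in a limited form. As written, the daily EGFRI-dose log is an instruction to one arm only, while adherence is tested between arms with no definition and no named source. If the diary feeds that endpoint in whole or in part, ascertainment of missed oral doses would differ by arm and could create or hide a difference.

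The size for this trial is unknown. The 59.5% and 25% rejection rates show only that unequal recording of this order could matter. They depend on invented recording rates, on the share of patients taking oral agents, and on an adherence outcome defined as any recorded missed dose. The conclusion also takes adherence to chemotherapy to include the EGFRI, which the protocol does not spell out.

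This concerns one secondary endpoint. The primary endpoint and the sample size are unaffected. The change should be made because it is cheap and missing daily records cannot be rebuilt afterwards.

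**What to change.** 1. Move the EGFRI-dose logging instruction into the all-patients paragraph of 4.2.1 and repeat it in 4.2.2.
2. Replace Appendix 2 with one arm-neutral diary: an EGFRI-dose field, moisturizer and sunscreen, and the same daily rash and symptom rows in both arms. Include the triamcinolone line for the steroid arm only.
3. State in 9.3 one definition of adherence, derived from the same source in both arms and covering oral and infused agents.

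The cost is a reworded paragraph, a revised form, a short addition to 9.3, and slightly more diary work for controls. No extra visits are needed.

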4.3 Toxicity Management & Dose Delays/Modifications

Any patient who receives at least one dose of study therapy will be evaluable for toxicity endpoints. Any patient who develops any of the side effects listed in section 8.1.9 will be taken off of treatment with triamcinolone cream, but will be followed through the study for six weeks.

4.4 Concomitant Medications/Treatments

Patients must be on one of the following EGFR inhibitor drugs: erlotinib, cetuximab, panitumumab, afatinib or osimertinib.

4.5 Duration of Therapy

Patients will receive treatment for 6 weeks. If any patient is in the control arm and develops a papulopustular rash, they will be treated with topical triamcinolone 0.1% cream and or antibiotic treatment, oral doxycycline 100 mg or oral minocycline 100 mg twice daily, as is the standard of care. These participants will still be followed for the 6 week duration of study.

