Obtain demographic data, medical history, medication list, history of drug reactions, personal and family hx of acne/rosacea; perform complete skin exam; obtain standard digital photos of face, chest, and back; count baseline number of macules/papules/pustules on face, chest, and back; obtain optional nasal swab culture

Administer FACT-EGFRI-18 questionnaire

Randomly assigned 1:1

Initiate cetuximab, erlotinib, panitumumab, afatinib or osimertinib therapy Initiate topical triamcinolone 0.1% cream

Initiate cetuximab, erlotinib, panitumumab, afatinib or osimertinib therapy

At any time point, if grade 2 or greater rash develops, initiate treatment as deemed necessary, such as topical steroids or oral antibiotics. Participants will still be followed for the six week duration of study.

incidence and severity

Skin exam. di

Adverse side effects assessment, FACT-EGFRI-18, review of patient diary incidence and severity
Adverse side effects assessment, FACTEGFRI-18, review of patient diary

nt of rash

Week 4

Skin exam, digital photos, assessment of rash

Week 6

Skin exam, digital photos, assessment of rash incidence and severity
Adverse side effects assessment, FACT-EGFRI-18, review of patient diary; obtain optional nasal swab

Week 4

Skin exam, digital photos, assessment of rash

Week 6

Skin exam, digital photos, assessment of rash incidence and severity

Adverse side effects assessment, FACT-EGFRI-18, review of patient diary; obtain optional nasal swab

STUDY SUMMARY

Title	A Randomized Phase II Study of Topical Steroids as Preemptive Therapy for Epidermal Growth Factor Receptor Inhibitor-Induced Papulopustular Eruption		
Short Title	A Study of Topical Steroids as Preemptive Therapy EGFR Inhibitor- Induced Papulopustular Eruption		
Version	07-02-2019		
Study Design	Randomized Control Trial		
Study Center(s)	Robert H. Lurie Cancer Center		
Objectives	To determine the efficacy of preemptive treatment with topical steroids (triamcinolone 0.1% cream for application to face, chest and back) when administered concomitantly for 6 weeks with erlotinib, cetuximab, panitumumab, afatinib or osimertinib to prevent papulopustular eruptions.		
Sample Size	84		
Diagnosis & Key Eligibility Criteria	Patients must have a histologically or cytologically confirmed cancer diagnosis for which EGFRI treatment is indicated, and must be starting treatment with cetuximab, erlotinib, panitumumab, afatinib or osimertinib.		

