1.0 INTRODUCTION - BACKGROUND & RATIONALE

1.1 Disease Background

The epidermal growth factor receptor (EGFR) is a member of a family of membrane receptors with tyrosine kinase activity that is expressed in cells from all three embryonic layers, but particularly in cells of epithelial origin, including the skin, respiratory tract, gastrointestinal tract, urinary tract, and liver.¹ Because EGFR overexpression plays a role in the malignant behavior of cells and is overexpressed in human tumors of epithelial origin, several biologic agents targeting the EGFR have emerged over the past decade as a robust therapy against several malignancies, including non-small cell lung, colorectal, head and neck, and pancreatic carcinomas.¹The first EGFR inhibitor was FDA-approved in 2004, and currently there are three tyrosine kinase inhibitors (TKIs) (erlotinib [Tarceva®], lapatinib [Tykerb®], afatinib [Gilotrif®]) and two monoclonal anti-EGFR antibodies (cetuximab [Erbitux®], panitumumab [Vectibix®]) that are commercially available.

Because EGFR inhibitors (EGFRIs) specifically target pathways that are crucial for cancer cell growth and survival, as opposed to targeting all replicating cells, they are associated with different adverse systemic side effects in comparison with standard chemotherapeutic drugs.² Specifically, EGFRIs are associated with a distinct class-specific toxicity profile, most evident in tissues that are crucially dependent on EGFR signaling for normal function, including the skin and hair follicles.³ Patients treated with EGFRIs experience cutaneous toxicities that can be severe, and these side effects often lead to reduction and even cessation of treatment. Depending upon the specific EGFRI and the dose, a characteristic papulopustular eruption can develop in as many as 45-90% of patients.^{4,5} While it most frequently involves the sebaceous gland-bearing regions of the body, i.e. the scalp, face, chest and upper back, the eruption can extend to additional sites in severe cases.⁵ The rash commonly starts as a sensory disturbance with erythema and edema (weeks 0 to 1), followed by a progression to an acne-like appearance with central pustule formation (weeks 1 to 3). Crusting then develops (weeks 3 to 5), and it often ends with erythematotelangiectatic changes (weeks 5 to 8).⁶

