Most recently, a phase II Skin Toxicity Evaluation Protocol with Panitumumab (STEPP) trial investigated the effectiveness of oral doxycycline (100 mg twice daily) by randomizing 95 patients with metastatic colorectal cancer to either: (1) preemptive therapy (started 24 hours prior to initiation of panitumumab plus irinotecan or FOLFIRI [leucovorin, 5-fluorouracil, irinotecan], and continued daily through week 6); or (2) reactive therapy (started when symptoms of dermatologic toxicity first appeared). In addition to the doxycycline, the treatment regimen consisted of topical hydrocortisone 1% cream twice daily, sunscreen when going outdoors, and moisturizer to areas of xerosis. At week 6, preemptive treatment reduced the incidence rate of grade 2 or greater skin toxicities by over 50% when compared to reactive treatment. The incidence of grade 2 or greater skin toxicities during the 6-week skin treatment period was 29% and 62% for the preemptive and reactive groups, respectively. Additionally, the time to severe skin toxicity was significantly delayed by preemptive skin treatment. At 6 weeks, the event- (grade 2 or greater skin toxicity) free probabilities were 70% and 38% for the preemptive and reactive arms, respectively.

Overall, two of these three controlled studies suggest that the tetracycline derivatives can lessen the severity, and possibly prevent, EGFRI-induced papulopustular eruptions. The beneficial effects of tetracyclines can be attributed to their anti-inflammatory effects, as well as their tissue-protective properties, such as their inhibition of neutrophil and eosinophil chemotaxis²⁵. In addition, tetracyclines may have antineoplastic properties. In *in vitro* studies, doxycycline has been shown to have anti-angiogenic properties and induces apoptosis in colorectal cancer cells.²⁶ Thus, it is theoretical that doxycycline may have beneficial effects against tumor activity.

Currently, the standard of care according to current interdisciplinary guidelines for management of the EGFRI-associated papulopustular eruption includes initiation of either oral doxycyline 100 mg twice daily or oral minocycline 100 mg twice daily at the onset of grade 2 or greater severity of rash. ¹⁹ The most common side effects associated with the tetracycline antibiotics are nausea, vomiting, and diarrhea. Often times, these gastrointestinal-related side effects may lead to cessation of treatment with these antibiotics.

Topical Steroids

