8.1.9 Side effects

- Blistering, burning, crusting, dryness, or flaking of the skin
- Thinning of the skin with easy bruising
- Itching, scaling, severe redness of the skin
- Redness and scaling around the mouth
- Acne or pimples
- Burning and itching of the skin with blisters
- Burning, itching, and pain in hairy areas, or pus at root ofhair
- Increased hair growth on forehead, back, arms, legs
- Lightening of normal skin color
- · Lightening of treated areas of dark skin
- Reddish purple lines on arms, face, legs, trunk, or groin
- Softening of the skin

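### Section 4.5 omits the schema's grade 2 threshold for rescuing controls, and section 4.3 can be read as stopping the cream for the study eruption; both could dilute the grade 2+ contrast

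*Combined protocol and SAP*

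**What the plan says.** **Rescue.** The schema at the front of the combined document gives one rule with a grade: "At any time point, if grade 2 or greater rash develops, initiate treatment as deemed necessary, such as topical steroids or oral antibiotics". Section 4.5 addresses the control arm only and gives no grade: "If any patient is in the control arm and develops a papulopustular rash, they will be treated with topical triamcinolone 0.1% cream". The same sentence goes on to allow doxycycline or minocycline as well or instead, and calls this standard of care. Section 1.2 places standard-of-care use of those two antibiotics "at the onset of grade 2 or greater severity of rash".

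**Stopping the cream.** Section 4.3 says: "Any patient who develops any of the side effects listed in section 8.1.9 will be taken off of treatment with triamcinolone cream". Follow-up then continues to six weeks. The 8.1.9 list includes "Acne or pimples". Section 1.1 describes the EGFRI eruption as starting with a sensory disturbance, erythema and edema, "followed by a progression to an acne-like appearance with central pustule formation (weeks 1 to 3" of treatment.

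**Endpoint.** Sections 2.1, 6.2 and 9.1 define the primary endpoint as the percentage of patients with grade 2 or greater rash. Table 1 defines grade 1 as papules or pustules on less than 10% of body surface. Maximum severity is a secondary endpoint (2.2.1, 6.3.1).

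**The concern.** A grade 1 eruption meets the trigger in 4.5 but not the one in the schema, so two clinicians following different pages would manage the same control patient differently. Under 4.5 that patient can receive the trial's own active drug before the endpoint is reached. Under a literal reading of 4.3, a steroid patient with the same early eruption loses the drug.

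The first change may lower the control arm's grade 2+ rate and the second may raise the steroid arm's. Both reduce the difference that the trial is meant to detect. A null result on grade 2+ rash would then be hard to interpret: it could reflect rescue and stopping practice rather than an ineffective cream.

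**Working it through.** **1. Rescue triggers side by side**

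| Source | Trigger | Treatment | Arm |
|---|---|---|---|
| Schema | Grade 2 or greater | Topical steroids or oral antibiotics, as needed | No arm restriction stated |
| 4.5 | A papulopustular rash, no grade | Triamcinolone 0.1% and/or doxycycline or minocycline | Control |
| 1.2, standard of care | Grade 2 or greater | Doxycycline or minocycline | Not arm-specific |

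The standard-of-care phrase in 4.5 can bring in the 1.2 threshold for the antibiotics. It cannot do so for triamcinolone, because 1.2 states no threshold for a topical steroid. The only grade given for topical steroids is in the schema.

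**2. Stopping rule.** Section 4.3 has no grade and no attribution condition. Section 7.2.1 does require at least possible relatedness, but for which adverse events are collected. The attribution categories in 7.3.2 serve expedited reporting. Neither is linked to stopping the cream.

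**3. The plan's own power.** Inputs from 9.2: 84 patients, 3% loss, 75% control versus 45% steroid, 80% power. Two-sided 5% is from the study summary and 1:1 allocation from the schema.

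- n per arm = 84 × 0.97 / 2 = 40.74.
- Power = Φ{[Δ√n − 1.96√(2p̄(1−p̄))] / √(p₁(1−p₁) + p₂(1−p₂))}, with p̄ = 0.60.
- Δ√n = 0.30 × √40.74 = 1.915; 1.96 × √0.48 = 1.358; √(0.1875 + 0.2475) = 0.660.
- z = (1.915 − 1.358) / 0.660 = 0.844, so power = 80.1%. The stated 80% reproduces.

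**4. Illustrations of dilution.** The documents give no early-rescue or early-stopping rates, so every rate here is assumed. The figures also treat 75% and 45% as grade 2+ rates, whereas 9.2 describes them as rash incidence without a grade.

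Let f be the share of eventual grade 2+ controls rescued at grade 1, and e the relative reduction in their chance of reaching grade 2. Control rate = 0.75 × (1 − f × e).

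| Assumption | Control | Steroid | Power |
|---|---|---|---|
| No dilution | 75% | 45% | 80.1% |
| f = 0.10, e = 0.10 | 74.25% | 45% | 77.8% |
| f = 0.10, e = 0.20 | 73.5% | 45% | 75.4% |
| f = 0.25, e = 0.10 | 73.1% | 45% | 74.2% |
| f = 0.25, e = 0.20 | 71.25% | 45% | 67.7% |
| 10% of steroid patients stop and lose half of the 30-point benefit: 0.45 + 0.10 × 0.5 × 0.30 | 75% | 46.5% | 76.0% |
| f = 0.10, e = 0.20, plus the stopping case | 73.5% | 46.5% | 70.8% |

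**5. What is not affected.** The Mantel-Haenszel comparison in 9.3 is of eruption of any severity by six weeks. A patient with a first rash is already an event there, so rescue or stopping afterwards cannot change the result.

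**The case against.** **Section 4.5 may be shorthand for the schema.** It invokes standard of care, names the antibiotics that 1.2 ties to grade 2 or greater, and ends with a follow-up sentence much like the schema's. This stands for the antibiotics. It does not settle when the study cream starts.

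**Section 4.3 already implies causation.** It speaks of side effects, and 8.1.9 lists those of triamcinolone. Section 1.2 separates the EGFRI eruption from acne: no comedones and mainly pustular. The schema's use of topical steroids for a grade 2+ rash also fits badly with a rule that the eruption ends steroid use. All this stands. A reader might infer that 4.3 orders the cream stopped for the study eruption; the documents do not support that. The defect is an ambiguity: papules or pustules on treated skin in the first weeks could be taken as meeting the rule, and nothing written says otherwise.

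**Early reactive treatment is a legitimate comparator.** Section 2.2.1 calls the control a reactive treatment group. In the cited panitumumab trial the comparator was "reactive therapy (started when symptoms of dermatologic toxicity first appeared", and grade 2 or greater toxicity still "was 29% and 62% for the preemptive and reactive groups, respectively". At 40.74 per arm, 62% versus 29% would have 86.3% power. So early rescue need not remove a contrast. But that trial used doxycycline plus hydrocortisone 1%, enrolled a different population, and had no arm treated only from grade 2. It cannot show how much early rescue dilutes, or that it does not.

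**Conclusion.** The point holds as a wording conflict in 4.5 and an ambiguity in 4.3. For the study cream, 4.5 lacks the grade threshold that the schema supplies. In 4.3 there is no written condition to keep the EGFRI eruption from being taken for a cream side effect. Followed literally, both act before the grade 2+ endpoint and shrink the contrast on that endpoint and on maximum severity.

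Two stronger conclusions might be drawn, and neither is supported:

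- **That the trial is tilted toward a false positive.** Both changes push toward no difference.
- **That a specific amount of power is lost.** The illustrated range, from 80.1% down to 67.7%, rests on assumed rescue and stopping rates. It applies only if 75% and 45% are grade 2+ rates. The true loss depends on which page clinicians follow and could be negligible.

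Severity is minor to moderate. The text is unclear at a point that bears on the primary endpoint, but sensible readings exist that would prevent the harm.

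**What to change.** 1. **Section 4.5:** state that rescue starts at grade 2 or greater, as in the schema, and only after the date and CTCAE grade of the rash have been recorded.
2. **Section 4.3:** stop the cream only for 8.1.9 effects that the investigator judges at least possibly related to triamcinolone. State that the EGFRI papulopustular eruption alone is not a reason to stop. Keep the investigator's discretion under 4.7 to withdraw treatment for safety.
3. **Recording:** 4.7 already requires the reason for discontinuation on the eCRF. Add the date and CTCAE grade at rescue or cream discontinuation, if the forms (not shown) do not already hold them. For patients already rescued or stopped below grade 2, list number, date and grade by arm.

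**Cost:** a short wording amendment and an eCRF check. Sample size, visits and the planned tests do not change. There are two downsides. Attributing a papule or pustule to the cream or to the EGFRI needs investigator judgement in an open-label trial, since controls receive no preemptive treatment and no vehicle is described. Control patients with a grade 1 rash would wait until grade 2 for rescue, as the schema already provides.
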